Appendix 5**
**Preferred terms for solicited AEs and preferred terms in
aggregated terms**

Trial ID: MT-18

Investigational Medicinal Product: HDM SLIT-tablet

Phase: IV

EudraCT No.: 2020-000446-34

Sponsor: Global Clinical Development
ALK-Abelló A/S
[name]
[contact]

Document Status: Final

Date: 06-Feb-2020

Version: 1.0

Confidential

Property of ALK

May not be used, divulged, published or otherwise disclosed without the written consent of
ALK

Table of Contents

1	Solicited signs/symptoms.....	3
2	Systemic allergic reactions including anaphylactic reactions	4
3	Local swelling or oedema of the mouth and/or throat.....	8
4	Medication errors	9
5	Drug abuse, misuse and overdose	14

1 Solicited signs/symptoms

Preferred terms (PTs) representing the solicited signs/symptoms have been selected (MedDRA 22.1, PTs will be updated to current MedDRA version at the time of reporting). All AEs with these PTs occurring during the 28 days treatment period will be defined as solicited AEs.

Solicited signs/symptoms patient card term	Solicited AE PT
Food taste different	Dysgeusia
Mouth ulcer/sore in the mouth	Mouth ulceration
Swelling of the uvula/back of the mouth	Enlarged uvula Oedema uvula Palatal swelling Palatal oedema Mouth swelling Oedema mouth
Itching of the mouth	Oral pruritus
Itching in the ear	Ear pruritus
Swelling of the lips	Lip swelling Lip oedema
Swelling of the tongue	Swollen tongue Tongue oedema
Tongue pain	Glossodynia
Tongue ulcer/sore on the tongue	Tongue ulceration
Throat irritation/tickle	Throat irritation
Throat swelling	Pharyngeal edema Pharyngeal swelling
Stomach pain	Abdominal pain upper Abdominal pain
Nausea (feel like throwing up)	Nausea
Vomiting	Vomiting
Diarrhea	Diarrhea

2 Systemic allergic reactions including anaphylactic reactions

Cases of possible systemic allergic reaction and/or anaphylaxis are identified by using the following criteria (MedDRA version 22.1, PTs will be updated to current MedDRA version at the time of reporting):

Standardised MedDRA Query (SMQ):

- Anaphylactic reaction, including algorithm:
 - A narrow term from category A;
 - A term from category B – (upper airway/respiratory) AND a term from category C – (angioedema/urticaria/pruritus/flush). Events co-occurring within 24 hours.
 - A term from category D – (cardiovascular/hypotension) AND a term from category B – (upper airway/respiratory) OR a term from category C (angioedema/urticaria/pruritus/flush). Events co-occurring within 24 hours.

PT	Scope	Category
Anaphylactic reaction	Narrow	A
Anaphylactic shock	Narrow	A
Anaphylactic transfusion reaction	Narrow	A
Anaphylactoid reaction	Narrow	A
Anaphylactoid shock	Narrow	A
Circulatory collapse	Narrow	A
Dialysis membrane reaction	Narrow	A
Kounis syndrome	Narrow	A
Procedural Shock	Narrow	A
Shock	Narrow	A
Shock symptom	Narrow	A
Type I hypersensitivity	Narrow	A
Acute respiratory failure	Broad	B
Asthma	Broad	B
Bronchial oedema	Broad	B
Bronchospasm	Broad	B
Cardio-respiratory distress	Broad	B
Chest discomfort	Broad	B
Choking	Broad	B
Choking sensation	Broad	B
Circumoral oedema	Broad	B

PT	Scope	Category
Cough	Broad	B
Cyanosis	Broad	B
Dyspnoea	Broad	B
Hyperventilation	Broad	B
Irregular breathing	Broad	B
Laryngeal dyspnoea	Broad	B
Laryngeal oedema	Broad	B
Laryngospasm	Broad	B
Laryngotracheal oedema	Broad	B
Mouth swelling	Broad	B
Nasal obstruction	Broad	B
Oedema mouth	Broad	B
Oropharyngeal oedema	Broad	B
Oropharyngeal spasm	Broad	B
Oropharyngeal swelling	Broad	B
Pharyngeal oedema	Broad	B
Pharyngeal swelling	Broad	B
Respiratory arrest	Broad	B
Respiratory distress	Broad	B
Respiratory failure	Broad	B
Reversible airways obstruction	Broad	B
Sensation of foreign body	Broad	B
Sneezing	Broad	B
Stridor	Broad	B
Swollen tongue	Broad	B
Tachypnoea	Broad	B
Throat tightness	Broad	B
Tongue oedema	Broad	B
Tracheal obstruction	Broad	B
Tracheal oedema	Broad	B
Upper airway obstruction	Broad	B
Wheezing	Broad	B
Acquired C1 inhibitor deficiency	Broad	C

PT	Scope	Category
Allergic oedema	Broad	C
Angioedema	Broad	C
Circumoral swelling	Borad	C
Erythema	Broad	C
Eye oedema	Broad	C
Eye pruritus	Broad	C
Eye swelling	Broad	C
Eyelid oedema	Broad	C
Face oedema	Broad	C
Flushing	Broad	C
Hereditary angioedema with C1 esterase inhibitor deficiency	Broad	C
Injection site urticaria	Broad	C
Lip oedema	Broad	C
Lip swelling	Broad	C
Nodular rash	Broad	C
Ocular hyperaemia	Broad	C
Oedema	Broad	C
Oedema blister	Broad	C
Periorbital oedema	Broad	C
Periorbital swelling	Broad	C
Pruritus	Broad	C
Pruritus allergic	Broad	C
Rash	Broad	C
Rash erythematous	Broad	C
Rash pruritic	Broad	C
Skin swelling	Broad	C
Swelling	Broad	C
Swelling face	Broad	C
Swelling of eyelid	Broad	C
Urticaria	Broad	C
Urticaria papular	Broad	C
Blood pressure decreased	Broad	D

PT	Scope	Category
Blood pressure diastolic decreased	Broad	D
Blood pressure systolic decreased	Broad	D
Cardiac arrest	Broad	D
Cardio-respiratory arrest	Broad	D
Cardiovascular insufficiency	Broad	D
Diastolic hypotension	Broad	D
Hypotension	Broad	D

3 Local swelling or oedema of the mouth and/or throat

Preferred terms (PTs) indicating swelling or oedema in the mouth and/or throat have been selected (MedDRA 22.1, PTs will be updated to current MedDRA version at the time of reporting). AEs with these PTs will be used for summary of the ESI local swelling or oedema if the mouth and/or throat.

PTs for identification of laryngo-pharyngeal swellings/oedemas
Dysphagia
Dysphonia
Epiglottic oedema
Laryngeal dyspnoea
Laryngeal obstruction
Laryngeal oedema
Laryngotracheal oedema
Mouth swelling
Oedema mouth
Oropharyngeal swelling
Oropharyngeal oedema
Palatal oedema
Palatal swelling
Pharyngeal oedema
Pharyngeal swelling
Sensation of foreign body
Suffocation feeling
Swollen tongue
Throat tightness
Tongue oedema
Tracheal oedema

4 Medication errors

Preferred terms (PTs) related to medication errors have been selected by using the following criteria (MedDRA version 22.1, PTs will be updated to current MedDRA version at the time of reporting):

Standardised MedDRA Query (SMQ):

- Medication errors

PTs for identification of medication errors
Accidental device ingestion
Accidental device ingestion
Accidental device ingestion by a child
Accidental exposure to product
Accidental exposure to product by child
Accidental exposure to product packaging
Accidental exposure to product packaging by child
Accidental overdose
Accidental poisoning
Accidental underdose
Accidental use of placebo
Booster dose missed
Circumstance or information capable of leading to device use error
Circumstance or information capable of leading to medication error
Contraindicated device used
Contraindicated product administered
Contraindicated product prescribed
Deprescribing error
Device dispensing error
Device monitoring procedure not performed
Device programming error
Device use confusion
Device use error
Dietary supplement prescribing error
Discontinued product administered
Documented hypersensitivity to administered product
Dose calculation error
Drug administered in wrong device
Drug dispensed to wrong patient
Drug dose omission by device
Drug dose titration not performed
Drug monitoring procedure incorrectly performed

PTs for identification of medication errors
Drug monitoring procedure not performed
Drug titration error
Duplicate therapy error
Expired device used
Expired product administered
Exposure via direct contact
Exposure via eye contact
Exposure via skin contact
Extra dose administered
Failure of child resistant mechanism for pharmaceutical product
Failure to suspend medication
Inadequate aseptic technique in use of product
Inappropriate schedule of product administration
Incomplete course of vaccination
Incorrect disposal of product
Incorrect dosage administered
Incorrect dose administered
Incorrect dose administered by device
Incorrect dose administered by product
Incorrect drug administration rate
Incorrect product administration duration
Incorrect product dosage form administered
Incorrect product formulation administered
Incorrect route of product administration
Intercepted accidental exposure to product by child
Intercepted medication error
Intercepted product administration error
Intercepted product dispensing error
Intercepted product monitoring error
Intercepted product preparation error
Intercepted product prescribing error
Intercepted product selection error
Intercepted product storage error
Intercepted wrong patient selected
Labelled drug-disease interaction medication error
Labelled drug-drug interaction medication error
Labelled drug-food interaction medication error
Lack of administration site rotation
Lack of application site rotation
Lack of infusion site rotation
Lack of injection site rotation

PTs for identification of medication errors

Lack of vaccination site rotation
Medical device monitoring error
Medication error
Multiple use of single-use product
Paravenous drug administration
Poor quality product administered
Product administered at inappropriate site
Product administered to patient of inappropriate age
Product administration error
Product appearance confusion
Product barcode issue
Product confusion
Product design confusion
Product dispensing error
Product dosage form confusion
Product dose omission
Product label confusion
Product monitoring error
Product name confusion
Product packaging confusion
Product preparation error
Product prescribing error
Product selection error
Product storage error
Product substitution error
Recalled product administered
Single component of a two-component product administered
Therapeutic drug monitoring analysis incorrectly performed
Therapeutic drug monitoring analysis not performed
Transcription medication error
Transfusion with incompatible blood
Unintentional use for unapproved indication
Vaccination error
Wrong device used
Wrong dosage form
Wrong dosage formulation
Wrong dose
Wrong drug
Wrong patient received product
Wrong product administered
Wrong product procured

PTs for identification of medication errors
Wrong product stored
Wrong rate
Wrong schedule
Wrong strength
Wrong technique in device usage process
Wrong technique in product usage process
Complication of device insertion
Complication of device removal
Complication of drug delivery system removal
Contraindication to medical treatment
Contraindication to vaccination
Device adhesion issue
Device connection issue
Device difficult to use
Device infusion issue
Device malfunction
Device use issue
Device-device incompatibility
Drug delivery system issue
Drug delivery system malfunction
Exposure to contaminated device
Exposure via contaminated device
Exposure via ingestion
Exposure via inhalation
Exposure via partner
Exposure via unknown route
Implantation complication
Injury associated with device
Interchange of vaccine products
Needle issue
Occupational exposure to product
Occupational exposure to radiation
Overdose
Poor quality device used
Prescribed overdose
Prescribed underdose
Product adhesion issue
Product administration interrupted
Product commingling
Product communication issue
Product compounding quality issue

PTs for identification of medication errors

- Product dispensing issue
- Product dosage form issue
- Product dropper issue
- Product expiration date issue
- Product identification number issue
- Product label issue
- Product label on wrong product
- Product lot number issue
- Product packaging difficult to open
- Product packaging issue
- Product preparation issue
- Product prescribing issue
- Product reconstitution quality issue
- Product use complaint
- Product use in unapproved indication
- Product use in unapproved therapeutic environment
- Product use issue
- Radiation overdose
- Radiation underdose
- Syringe issue
- Treatment noncompliance
- Underdose
- Unintentional medical device removal

5 Drug abuse, misuse and overdose

Preferred terms (PTs) related to drug abuse, misuse and overdose have been selected by using the following criteria (MedDRA version 22.1):

Standardised MedDRA Query (SMQ):

- Drug abuse and dependence

PTs for identification of drug abuse, misuse and overdose
Dopamine dysregulation syndrome
Drug abuse
Drug abuser
Drug dependence
Drug dependence, antepartum
Drug dependence, postpartum
Drug use disorder
Drug use disorder, antepartum
Drug use disorder, postpartum
Intentional overdose
Intentional product misuse
Maternal use of illicit drugs
Neonatal complications of substance abuse
Substance abuse
Substance abuser
Substance dependence
Substance use disorder
Accidental overdose
Dependence
Disturbance in social behaviour
Drug detoxification
Drug diversion
Drug level above therapeutic
Drug level increased
Drug screen
Drug screen positive
Drug tolerance
Drug tolerance decreased
Drug tolerance increased
Intentional product use issue
Medication overuse headache
Narcotic bowel syndrome
Needle track marks
Overdose

PTs for identification of drug abuse, misuse and overdose

Prescription drug used without a prescription

Prescription form tampering

Reversal of opiate activity

Substance use

Substance-induced mood disorder

Substance-induced psychotic disorder

Toxicity to various agents

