Primary completion date	Date of the last data collection for the primary endpoint (ClinicalTrials.gov), which is the date of the last contact (FU-TC) for the last subject in the trial globally
Solicited AE	A pre-specified AE recorded by the investigator based on the signs/symptoms reported in the subject's diary during the 28 days of treatment

Source documents	Source documents are original documents, data, and records from which the subjects' electronic case report form (eCRF) data are obtained. These include, but are not limited to, hospital records (from which medical history and concomitant medication may be summarised into the eCRF), clinical and office charts, laboratory and pharmacy records, diaries, microfiches, radiographs, and correspondence
Systemic allergic reaction	Allergic reactions occurring after exposure to an allergen with symptoms from one or more organ system (skin, mucosal, respiratory, cardiovascular or gastrointestinal) not related to the administration site. Systemic allergic reactions can occur in different grades with the most severe reactions being anaphylaxis
Systemic corticosteroids	Oral, intramuscular, or intravenously administered corticosteroids
TEAE	TEAEs are defined as adverse events with start date on or after the time of first IMP administration and no later than 7 days after last IMP administration
Trial completion	The trial is completed once the integrated clinical trial report (ICTR) is signed
Subject discontinuation date	Date of subject trial discontinuation. In case of subjects lost to follow-up, the discontinuation date is defined as the date the investigator/sponsor decides to discontinue the subject

Protocol versions

Date	Version	Description of document	Rationale for amendment
06-Feb-2020	1.0	Final Protocol	N/A
08-Apr-2020	2.0	
Amendment 1: Amendment to address:
 
• risks associated with the COVID-19 pandemic• specific allergen used in the Skin Prick Test (SPT). 
The amendment applies to all countries. There are no changes affecting subject information and assent forms.
	
Amendment is done to address the EMA recommendations in the Guidance on the Management of Clinical Trials during the COVID-19 (Coronavirus) pandemic Version 2 (27/03/2020).
 
In addition, allergen for the SPT, is revised, please refer to rationale in the table below.

Section # and name	Description of change	Brief rationale

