2.3 Secondary endpoints

- At least one solicited TEAE
- At least one IMP-related adverse event (AE)
- At least one treatment-emergent serious adverse event (SAE)

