12.3 Collection, recording and reporting of AEs

At each contact with the trial site, the subject must be asked about AEs in an objective manner such as "Have you experienced any problems since the last contact?".

AEs must be recorded on the AE form. One single AE form must be used per AE from start to resolution. For SAEs, the SAE form must also be filled in.

In case of concomitant medication for treatment of the AE, the concomitant medication form must be filled in.

If the same type of AE occurs more than 1 day in a row with the same pattern and severity (e.g. itching in the mouth for 5-10 minutes after intake of IMP) it is considered a recurrent AE. The AE form should be filled in with the start date and the description. Once the AE does no longer reoccur after IMP intake, the AE form should be completed with a stop date and the event should be marked as recurrent in the eCRF. If the AE then re-appears on a subsequent day or if the AEs changes in severity, a new AE form should be filled in. For recurrent events, the investigator should ask the patient about approximate daily duration and record this in the eCRF.

The investigator should record the diagnosis, if available. If no diagnosis is available, the investigator should record each sign and symptom as individual AEs. Further, the diagnosis of the underlying disease should be reported instead of a procedure performed due to the disease (e.g. if a subject undergoes surgery due to appendicitis, appendicitis (and not the surgery performed) should be reported).

The AE start time of AEs that occur on V2 will be recorded in source documents and entered into the eCRF.

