12.3.1 Solicited AEs

The diary (See Appendix 4) will be used by the subject to help remember details and dates, when discussing AEs and concomitant medication with the investigator at the visits.

The diary lists 15 specific signs/symptoms, identified as local side effects of sublingual immunotherapy (Passalacqua et al. 2013). These local side effects will be collected on a daily basis by the subject during the 28 days of treatment (section 11.16).

See Appendix 5 for preferred terms used (PT) to identify solicited AEs.

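### Solicited TEAE is defined by diary origin in one place and by a preferred-term list in another, and the list omits two oropharyngeal swelling terms that the same appendix uses elsewhere

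*Combined protocol and SAP*

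**What the plan says.** Section 2.3 lists "At least one solicited TEAE" as a secondary endpoint, and the synopsis places it among the key secondary endpoints. Section 15.8.1 will report the number and proportion of subjects with an exact 95% confidence interval, and tabulate the events by SOC and PT. Neither section says how a solicited event is recognised.

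The definition is given in three other places:

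- Table of definitions: "A pre-specified AE recorded by the investigator based on the signs/symptoms reported in the subject's diary during the 28 days of treatment".
- Section 12.3.1 describes daily collection of 15 symptoms in the diary, then adds: "See Appendix 5 for preferred terms used (PT) to identify solicited AEs".
- Appendix 5 section 1 maps the 15 diary items to PTs and states: "All AEs with these PTs occurring during the 28 days treatment period will be defined as solicited AEs".

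Appendix 5 section 3 holds a second list, for the event of special interest, introduced with "Preferred terms (PTs) indicating swelling or oedema in the mouth and/or throat have been selected". Appendix 5 section 2 holds the terms for systemic allergic reactions.

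**The concern.** The Table of definitions makes the source of the report a condition; Appendix 5 section 1 makes only the code and the 28-day window a condition. These are not the same set of events, and the statistical section does not say which applies.

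Separately, a PT rule captures the diary symptoms only if the list covers the terms to which they may be coded. The diary's throat swelling item maps to two pharyngeal terms only, and its uvula/back-of-mouth item to six uvular, palatal and mouth terms. The oropharyngeal swelling terms appear elsewhere in the same appendix but not here.

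At stake is what a descriptive secondary endpoint measures. Section 1.3 says that the secondary endpoints focus on pre-specified local events, so a reader will take the solicited-TEAE tables as the account of what the diary prompted.

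**Working it through.** **1. The plan's own figures.** The documents give no rate, precision target or expected count for solicited TEAEs. The only precision figure, in section 15.1, is a 0.95% upper limit of the two-sided 90% interval for 1 event in about 500 subjects. It reproduces: the exact limit is the 0.95 quantile of Beta(2, 499) = 0.945%. It does not depend on this endpoint.

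**2. The two definitions side by side.** Both use the 28-day treatment period, so they differ in source and code only. A listed PT can arise without a diary entry, because section 12.3 also requires an open question: "At each contact with the trial site, the subject must be asked about AEs in an objective manner".

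| AE within the 28 days | Table of definitions | Appendix 5 section 1 |
|---|---|---|
| Nausea reported only in answer to the open question | not solicited | solicited |
| Diary throat swelling, coded Pharyngeal swelling | solicited | solicited |
| Diary throat swelling, coded Oropharyngeal swelling or Oropharyngeal oedema | solicited if *pre-specified* refers to the diary items; not solicited if it refers to the PT list | not solicited |

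The wording does not settle the last row: the synopsis and section 11.16 apply *pre-specified* to the 15 symptoms, section 1.3 to AEs. The first row differs on either reading.

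**3. The two swelling lists.** Section 1 contains 24 PTs and section 3 contains 21. After the oedema/edema spelling is harmonised, 8 are shared: Mouth swelling, Oedema mouth, Palatal swelling, Palatal oedema, Pharyngeal swelling, Pharyngeal oedema, Swollen tongue, Tongue oedema. So 21 − 8 = 13 section 3 terms are absent from section 1. On a literal match it is 14, because section 1 spells Pharyngeal edema where sections 2 and 3 spell Pharyngeal oedema. The 13 fall into three groups:

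- Oropharyngeal swelling and Oropharyngeal oedema (2). Both are also in section 2, and both match the site named in the throat or back-of-mouth diary items.
- Laryngeal, laryngotracheal, epiglottic and tracheal oedema (4). These are swelling terms, but whether a diary item would lead to them is arguable.
- Dysphagia, Dysphonia, Laryngeal dyspnoea, Laryngeal obstruction, Sensation of foreign body, Suffocation feeling, Throat tightness (7). None is a swelling term or corresponds directly to a diary item.

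Only the first group is a clear gap.

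**4. How a difference reaches the proportion.** Let *a* be the subjects counted only under Appendix 5 and *d* those counted only under the Table of definitions. With n = 250, the two proportions differ by (*a* − *d*)/250. Because the endpoint is at least one event per subject, a subject enters *a* or *d* only if no other AE of that subject qualifies under the other rule. Opposite moves cancel: *a* = *d* = 5 gives 0, while *a* = 5 and *d* = 0 gives 5/250 = 2.0 points.

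To show the scale of a net move of 5 subjects, with assumed counts and exact 95% limits (0.025 quantile of Beta(x, n − x + 1), 0.975 quantile of Beta(x + 1, n − x)):

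- 125 to 130: 50.0% (43.6–56.4) to 52.0% (45.6–58.3)
- 150 to 155: 60.0% (53.6–66.1) to 62.0% (55.7–68.0)
- 200 to 205: 80.0% (74.5–84.8) to 82.0% (76.7–86.6)

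Neither the base rate nor the 5 comes from the documents.

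**5. How it reaches the tables.** The at-least-one structure protects the proportion, not the breakdown. Under the PT rule the solicited-TEAE table has no row for the two oropharyngeal terms, whatever else the subject reported.

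**The case against.** The strongest answer is that section 12.3.1 already joins the two texts: the diary is the collection tool and the PT list is the means of identification. That stands as a guide to what a programmer would probably do. A reader might infer that the endpoint's numerator is undetermined; section 12.3.1 does not support going that far. It leaves the Table of definitions describing another set, and section 15.8.1 silent.

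Second, section 3 serves a different purpose and is deliberately broad, so it is no benchmark for section 1. This also stands. A reader might infer that all 13 absent terms are omissions; on the comparison above only two clearly are. Whether a diary swelling would in fact be coded to those two rather than to a listed pharyngeal term cannot be known from the documents.

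Third, no safety report is lost. Such an AE still counts in the primary endpoint and is tabulated by SOC and PT, the section 3 terms feed the event-of-special-interest summary, and severe swelling has its own endpoint. That is correct, so a reading that throat-swelling reports vanish from the safety evaluation is not supported. They are missing only from the solicited-TEAE summaries.

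Fourth, a reader might add the instruction "The investigator should record the diagnosis, if available" as a further leak, since vomiting within a diagnosed illness would be coded outside the list. This is weak. Sections 11.16 and 12.3.1 present the diary items as local side effects of sublingual immunotherapy, and section 11.16 has them become AEs only after medical evaluation, so leaving out such a case fits the endpoint's intent.

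Finally, Appendix 5 says that the PTs will be updated to the current MedDRA version. That may resolve spelling. It does not commit the sponsor to adding terms.

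**Conclusion.** The point holds in a limited form. The Table of definitions and Appendix 5 section 1 define different sets of solicited AEs. Section 12.3.1 makes the PT list the probable rule, but no text states that it governs. Followed exactly, that list leaves a diary-reported throat or back-of-mouth swelling coded to Oropharyngeal swelling or Oropharyngeal oedema out of the solicited-TEAE proportion and tables.

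The size cannot be derived. For the proportion it is probably small, given the at-least-one structure and the frequent local events reported in section 1.2 (oral pruritus, throat irritation): most affected subjects would probably have another qualifying event. A shift of several percentage points would need an assumed number of reclassified subjects, nearly all moving in one direction, and the documents offer no basis for that. Section 15.8 specifies no hypothesis testing, so no error rate or power is involved, and the primary endpoint is unchanged. The case for acting is that the gap is specific and costs almost nothing to close.

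**What to change.** - In section 15.8.1, state that solicited TEAEs are identified by the Appendix 5 section 1 PT list, and reword the Table of definitions entry to match, with the diary described as the collection tool.
- Add Oropharyngeal swelling and Oropharyngeal oedema to Appendix 5 section 1, under the throat swelling and the uvula/back-of-mouth items as the coding group judges appropriate. Do not import the other section 3 terms wholesale; Dysphagia, Dysphonia and Throat tightness, for instance, are not diary items.
- Use one spelling of oedema across the appendix, so that a literal match to coded terms does not fail.

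The cost is two entries in one table and a few sentences, all possible before database lock and with no new data collection. A summary restricted to diary-reported events is optional as a sensitivity analysis. It would need diary origin to be recorded on the AE form, where the recording instructions in sections 11.16 and 12.3 describe no such field. Making diary origin the main rule is not clearly better, because an event reported by telephone would drop out if the paper diary were blank or lost.
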